1.1 Transmission, clinical presentation and diagnosis of COVID-19

The name of virus responsible for the COVID-19 outbreak, Severe Acute Respiratory Syndrome (SARS) coronavirus 2 (SARS-CoV-2), was chosen based on its genetic similarities with the coronavirus that caused the SARS outbreak in 2003.³ The exact origin of the virus is currently unknown.⁴ Existing literature supports that the novel β-Coronavirus (termed SARS-CoV-2) belongs to the family Coronaviridae, from the order Nidovirales, which are all enveloped, non-segmented positive-sense RNA viruses which may cause illness in humans and animals.^{5,6} The Coronaviridae family of viruses include causative viruses such as Severe Acute Respiratory Syndrome (SARS) and Middle Eastern Respiratory Syndrome (MERS).⁷ Much like influenza and other respiratory viruses, SARS-CoV-2 is primarily transmitted person-to-person through close inhalation of respiratory droplets formed during a cough, sneeze or exhale.⁸ People without the disease can also acquire the infection by touching surfaces contaminated by SARS-CoV-2, defined as fomite transmission.⁹ Clinical manifestations among adults include fever, cough, myalgia, headache and shortness of breath.¹⁰ Severe cases can result in life threatening pneumonia and acute respiratory distress syndrome.¹¹ The incubation period is estimated to be between 1 and 14 days, with 97.5% of cases developing symptoms within 10.5 days (95% Cl: 7.3-15.3) of infection.¹² Due to the small number of cases, it is not yet certain whether pregnancy and childbirth aggravate clinical presentation of COVID-19.

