3.6 Data Collection

3.6.1 Timing of Sample Collection

Upon admission to labour and delivery, and prior to delivery wherever possible, the following maternal sample types will be collected: nasopharyngeal or oropharyngeal swab, peripheral blood, ano-rectal swab and vaginal mucosa collected through a vaginal swab. At delivery, wherenever possible, we will collect an amniotic fluid sample through direct syringe aspiration. Should the maternal biological samples not be able to be collected prior to or during delivery, samples may be collected post-delivery, prior to discharge.

Immediately following delivery, we will collect cord blood and placenta samples (including submaniotic swab). Prior to discharge from the hospital, we will collect a neonatal nasopharyngeal swab sample (approximately 12-24 hours post-birth) and a breastmilk sample (nearest to first lactation as possible). The timing of sample

collection is summarized in **Table 2** presented below. Pathologists at each participating site will be requested to send the local placenta pathology report and slides (or scanned slides if slides are not feasible), collected as per standard of care.

Table 2. Timing of biological sample collection

	Timing of sample collection				
Biological sample	Prior to delivery	At delivery	Post deliver	ТY	
Maternal peripheral blood	Х				
Maternal nasopharyngeal or oropharyngeal swab	Х				
Maternal vaginal mucosa	X (swab prior to ۱ membranes, if				
Maternal ano-rectal swab	Х				
Amniotic fluid		Х			
Cord blood		X (from blood gases)			
Placenta (includes subamniotic swab)			X (ex vivo)		
Neonatal nasopharyngeal swab			X (12-24 hours po	st-birth)	
Breastmilk sample			Х		

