We will summarize the nucleic acid test results of all clinical samples collected (vaginal mucosa, amniotic fluid, cord blood, placenta, maternal nasopharyngeal/oropharyngeal and neonatal nasopharyngeal swab, breastmilk) to ascertain the possibility of intrauterine vertical transmission and post-partum feeding transmission. A positive test result reflects the presence of coronavirus in these clinical samples and will be indicative of possible mother-to-infant transmission. Laboratory test results however will be considered within the context of clinical observations and epidemiological data when making the final diagnosis decisions. In addition, binary logistic regression will be conducted to further investigate the association between coronavirus in placenta and the presence of fetal/neonatal complications.

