7.2 Benefits

The results of this may be beneficial to the participants and their infants, as COVID-19 case ascertainment information may be made available by sample analysis. While the results of sample analysis are research results, any results that may impact the care of a participants will be communicated to the staff and/or participant as they become available.

The study may not be directly beneficial to the participants or their infants in the cases of confirmed maternal diagnosis or negative sample ascertainment in infants, however the results of this study will help to guide clinicians in determining best mode of delivery and feeding practices in future COVID-19 pregnancies. Clarification of vertical transmission and mother-to-infant feeding transmission will provide essential information to health care providers globally for care management in pregnancy. The results from this study will be shared with health care professionals including general practitioners, obstetricians and gynecologists, policy makers and health care planners.

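### One infant swab at about 12–24 hours cannot support a conclusion for or against feeding transmission, yet sections 4.2.1 and 7.2 set the study up to draw one

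*Combined protocol and SAP*

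**What the plan says.** Section 4.2.1 pools the results of all clinical samples "to ascertain the possibility of intrauterine vertical transmission and post-partum feeding transmission". It reads a positive result in any of them as a sign of possible mother-to-infant transmission, and adds that laboratory results will be weighed against clinical and epidemiological information.

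Section 7.2 goes further. It says the results will "help to guide clinicians in determining best mode of delivery and feeding practices in future COVID-19 pregnancies", and that "Clarification of vertical transmission and mother-to-infant feeding transmission will provide essential information to health care providers globally". Section 9.2 describes the investigation of maternal-infant transmission as complete.

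On sampling, section 3.6.1 and Table 2 schedule a single "neonatal nasopharyngeal swab sample (approximately 12-24 hours post-birth", before discharge, and "a breastmilk sample (nearest to first lactation as possible". Amniotic fluid, cord blood and placenta are taken at delivery or directly after it. Section 4.2.2 tests antibodies in maternal and cord blood only.

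On timing of infection, section 1.1 states: "The incubation period is estimated to be between 1 and 14 days". It puts 97.5% of symptom onsets within 10.5 days of infection (95% CI 7.3–15.3).

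**The concern.** The protocol treats breastfeeding as a route of its own, separate from intrauterine and intrapartum transmission (section 1.6). To learn whether that route infects infants, the study needs an infant result that could turn positive because of feeding, and a way to tell such a positive from one caused by earlier exposure. The visible schedule and analysis plan supply neither.

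The likely report is a set of milk results beside mostly negative infant swabs. Readers could take that as reassurance that feeding does not transmit. Conversely, a positive milk sample with a positive swab could be taken as feeding transmission. The design supports neither inference, and section 7.2 offers the results as guidance for practice.

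**Working it through.** The plan has no figure to reproduce here. Section 4.1 anticipates 150 to upwards of 200 participants and says a usual power calculation cannot be done. The check is mainly one of timing.

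**1. What each sample on the infant or feeding side can show**

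| Sample | Timing (3.6.1, Table 2) | Taken after feeding can begin? | What a positive shows |
|---|---|---|---|
| Amniotic fluid | At delivery | No | Virus present by birth |
| Cord blood (RNA; antibodies under 4.2.2) | At or directly after delivery | No | Exposure before or at birth |
| Placenta, with subamniotic swab | Directly after delivery | No | Virus in placental tissue |
| Breastmilk | Before discharge, near first lactation | Not an infant sample | Virus in milk, not infection of the infant |
| Neonatal swab | About 12–24 hours | Yes | Virus in the infant's nasopharynx, route unknown |

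Only the swab could register an infant infection from feeding.

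**2. Time available for such an infection to show**

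Let the first feed occur t hours after birth (t ≥ 0) and the swab be taken s hours after birth, with s between 12 and 24. The interval from first feed to swab is s − t, which is at most s:

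- 12/24 = 0.5 day
- 24/24 = 1.0 day

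The plan does not fix the order of milk sample and swab, so the interval can be much shorter than this, or nil. Against section 1.1:

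- Stated minimum incubation: 1 day. The whole interval lies at or below it.
- Stated 97.5th percentile: 10.5 days. 0.5/10.5 = 4.8% and 1.0/10.5 = 9.5%, so the interval is about 5% to 10% of that time.

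**3. Reading a negative swab**

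By step 2, an infant infected through feeding would probably still test negative. A negative swab barely separates infection by feeding from no infection.

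**4. Reading a positive swab**

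A positive swab at 12–24 hours is compatible with in-utero, intrapartum or other early postnatal exposure, including droplets, as well as feeding. Section 4.2.1 gives no rule for assigning a route. Its reference to clinical and epidemiological context does not say how that context would do so.

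**5. What a run of negative swabs would bound**

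Assume one swabbed infant per participant and no positives. The exact one-sided 97.5% upper limit is 1 − 0.025^(1/n):

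- n = 150: 1 − 0.025^(1/150) = 2.4%
- n = 200: 1 − 0.025^(1/200) = 1.8%

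These limits apply to swab positivity at 12–24 hours, which mostly reflects exposure before or during birth. They are not limits on infection through feeding.

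**6. Mode of delivery**

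The only analysis by mode of delivery named in the supplied text is a subgroup analysis in the placental control section (3.9). It concerns placental pathology. The visible analysis plan contains no comparison of infant results by mode of delivery, although section 7.2 offers guidance on it.

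**The case against.** **The claim in 4.2.1 is modest.** It speaks of possibility, and section 2 speaks of transmission potential. Finding RNA in milk does bear on whether exposure through feeding is possible. This stands: a reader might infer that 4.2.1 promises to establish feeding transmission, and its wording does not say so. Section 7.2 has no such qualifier, however, and its talk of clarification and guidance on feeding needs infant outcomes.

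**The swab is not expressly assigned to feeding.** Section 4.2.1 pools the samples and names two routes. One can read milk as serving the feeding question and the rest as serving intrauterine or peripartum exposure. Nor does any passage say that a negative swab will count as absence of feeding transmission, so that intention should not be attributed to the plan. But if this benign reading is meant, nothing in the plan says so.

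**Incubation is not PCR positivity.** This also stands. A reader might be tempted to put a percentage on the swab's sensitivity to infection by feeding. The documents do not support one. A log-normal curve through the stated 97.5th percentile q needs a median m that is not given: sigma = ln(q/m)/1.96, and the share of onsets by 1 day is Φ(−ln m / sigma). With q = 10.5 days, an assumed m of 4 gives 0.24% and an assumed m of 3 gives 4.3%. With q at its stated upper limit of 15.3 days and m = 3, it is 9.3%. The result follows from the assumption, and it describes symptoms, not swab results. Earlier PCR positivity would weaken step 3 above but would leave the problem of assigning a route.

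**Later infant data may exist.** Section 3.6.4 links routine infant health data from BORN. But no later infant test is scheduled, and entry of COVID-19 data in BORN is optional for hospitals. The section numbering also jumps (3.6.4 to 3.9, and 4.2.2 to 6), and Appendix 1 is only a link. Statements that something is absent therefore apply to the supplied text alone.

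**Conclusion.** The point holds as a mismatch between stated conclusions and design. The plan names feeding transmission as a target and promises clarification and practice guidance. Its only scheduled infant test after feeding can begin is one swab, at most 0.5 to 1 day after first exposure, where the protocol's own minimum incubation is 1 day. Such a swab can support no conclusion for or against feeding transmission.

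That a feeding infection would be unlikely to show by then is a strong inference from the incubation range, not a documented fact, and it should be stated without a percentage. That a positive swab cannot be assigned to feeding does not depend on the inference. The mode-of-delivery claim is a separate and smaller gap: it has no matching infant analysis in the supplied text.

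**What to change.** - **Section 4.2.1.** Replace the reference to transmission by feeding with *presence of SARS-CoV-2 RNA in breastmilk (possible exposure through feeding)*. Add that the 12–24 hour swab informs in-utero or peripartum exposure, cannot distinguish feeding from other early exposure, and will support no conclusion for or against feeding transmission. The sentence on positive samples should be read subject to this.
- **Section 7.2.** Remove the claim to guide feeding practices, and narrow the sentence that promises clarification of feeding transmission. Changing only the first would leave the stronger claim in place.
- **Section 9.2.** Bring the description of a complete investigation into line.
- **Mode of delivery.** Either tabulate neonatal swab positivity by mode of delivery with exact confidence intervals, or remove the claim from 7.2. The table depends on mode being recorded in the study or linked data. Section 3.6.4 does not name it and the registry form is not reproduced, so this must be confirmed first.

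The cost is a wording amendment and at most one table, with no new samples or visits. The downside is a narrower stated claim.

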1.6 Mother-to-infant transmission

A crucial question that remains unanswered concerns whether SARS-CoV-2 can be transmitted by the infected pregnant mother to the infant during pregnancy, delivery or post-partum. Mother-to-infant transmission after maternal primary infection can occur during several time periods: intrauterine life via trans-placental viral transfer, delivery via ingestion or aspiration of vaginal secretions and postpartum through breastfeeding.³⁵ Due

to the scarce evidence currently available, the mother-to-child transmission capabilities of SARS-CoV-2 are not yet fully understood.

The small number of studies published thus far have not detected any evidence of vertical transmission from mother to fetus/infant^{13-15,36,37}; however, several newborns have tested positive for SARS-CoV-2 with case studies purporting the potential for vertical transmission.^{38–41} Further assessment is warranted as nearly all of the published findings included women infected during the third trimester of pregnancy and delivered by cesarean section.⁴²

The placenta is a superior example of a pregnancy diary and typically undergoes morphological changes in response to environmental stimuli. A case report of one COVID-19 positive pregnancy found that all collected biological specimens, including a placenta sample, tested negative for SARS-CoV-2.⁴³ Another review of three placentas found no morphological changes related to infection, though all of the women in this case series contracted the virus late in the third trimester and long after the placenta had undergone the bulk of its development.¹³ Furthermore, the role of the SARS-CoV-2 in various placental lesions (e.g., preeclampsia, abnormal placentation, intrauterine growth restriction [IUGR], and disruption of the chorionic membrane) has yet to be explored.

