3.3 Study Population

The study population will consist of pregnant women with confirmed COVID-19 at any point during pregnancy or suspected COVID-19 at time of delivery (as identified at local hospital), who will be delivering at a participating hospital within Ontario (current list of participating sites can be found in **Section 6.1**).

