3.9 COPE Network Site-Specific Placental Control Group

Evidence has shown that placentas not complicated by SARS-CoV-2 may also display pathological changes, thus highlighting the importance of including a sufficient number and variety of controls that would allow valid comparisons to be made. Subgroup analyses based on mode of delivery (cesarean section vs. vaginal) as well as maternal comorbidities (including but not limited to: preeclampsia, chronic hypertension, gestational and chronic diabetes, IUGR) will necessitate having sufficient controls with these characteristics.

In addition to the control participants recruited at TOH, COPE Network Sites with capacity to collaborate will be asked to send slides and pathology reports of placentas that, to the best of their knowledge, were not complicated by SARS-CoV-2. The following clinical indications may warrant placental pathology examination and would provide valuable control comparisons:

- Multiple births (both dichorionic and monochorionic)
- Preterm birth (<34 weeks of gestation)
- Placenta previa
- Elective Cesarean section delivery
- Clinical suspicion of abruption

• Compromised clinical condition of neonate (intensive care admission, cord pH<7.0, Apgar score of less than 5 at 5 minutes, ventilatory assistance, hematocrit less than 25%, hydrops fetalis, congenital anomalies)

- Fetal congenital anomalies
- Maternal cancer history

Placentas that were sent for pathology examination for reasons listed above, between April 2020 to July 2021 may be included in the 'pandemic' control group, and placentas sent to pathology prior to March 2019 (i.e., a year prior to the beginning of the pandemic) will be included in the 'pre-pandemic' control group for the purpose of comparing COVID-19 placental pathology to background pathology during both time points.

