4. STATISTICAL METHODS

4.1 Sample Size

Due to the novel nature of this study, the anticipated sample size it not yet known and therefore a typical power calculation cannot be performed. As of March 2nd 2021, Ontario has a total of 303, 763 confirmed COVID-19 cases reported.⁵⁰ Considering a total of approximately 13 major Ontario hospital sites will be involved in this study, our sample is anticipated to range anywhere from 150 to upwards of 200 participants.

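### The placental-virus regression has no sparse-data method: if few placentas test positive, ordinary logistic regression may give no finite odds ratio or an unstable one

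*Combined protocol and SAP*

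**What the plan says.** After describing how nucleic acid results will be summarised by sample type, section 4.2.1 adds one modelling sentence: "binary logistic regression will be conducted to further investigate the association between coronavirus in placenta and the presence of fetal/neonatal complications". It names no variant of logistic regression, so the natural reading is ordinary maximum likelihood. In the text available it does not define the complications, state the unit of analysis, list covariates, set a minimum number of positive placentas, or say what happens if the model cannot be fitted.

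On size, section 4.1 says that "our sample is anticipated to range anywhere from 150 to upwards of 200 participants" and that "a typical power calculation cannot be performed".

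No expected share of positive placentas is given anywhere. Section 1.6 reports one case in which "all collected biological specimens, including a placenta sample, tested negative for SARS-CoV-2", and says that the few published studies "have not detected any evidence of vertical transmission from mother to fetus/infant", although the same sentence goes on to mention newborns who tested positive. Section 3.3 admits "pregnant women with confirmed COVID-19 at any point during pregnancy or suspected COVID-19 at time of delivery".

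Timing and maternal data will be available. Section 3.6.2 records the date of diagnosis, or the date of COVID-19 admission when that is missing. Section 3.6.4 links to registry data on demographics, pre-existing conditions and obstetric complications. Section 4.2.1 assigns none of these to the regression.

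**The concern.** A logistic model with one binary exposure reproduces the 2x2 table of placental result by complication. If any cell is empty, or no placenta is positive, the maximum-likelihood odds ratio is zero, infinite or undefined, and its Wald interval means nothing. Women infected months before delivery, and women only suspected of infection, may well have virus-negative placentas, so few positives is a case the plan should be ready for.

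Tables that can be fitted are also a selected set. Take three positive placentas and a 20% complication rate. The table with no complications among the three is lost to separation. The smallest odds that can then be fitted among positives is 1:2 = 0.5, against 0.2/0.8 = 0.25 among negatives, which is already an odds ratio of about 2 with no true effect.

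Without a pre-specified fallback, the analyst would have to choose one after seeing the fit fail.

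**Working it through.** **Nothing to reproduce.** The plan gives no power, effect size, positivity or complication rate for this analysis, and its 150–200 is a recruitment expectation.

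**Inputs.** N = 150 and 200 (section 4.1). Placental positivity p = 1%, 2%, 5%, 10%, 20% (assumed). Complication rate c = 10%, 20%, 30% (assumed) and 41.1%, which is the preterm-birth rate cited in section 1.3, used as an upper proxy. True odds ratio 1 unless stated.

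**Chance of no finite odds ratio.** The number of positives k is Binomial(N, p). Given k ≥ 1, the positive row has an empty cell with probability c^k + (1−c)^k; an empty cell in the much larger negative row is negligible here. Adding the case k = 0 and summing over k gives

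P = (1 − p(1−c))^N + (1 − pc)^N − (1−p)^N.

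For N = 150, p = 2%, c = 20%: 0.984^150 + 0.996^150 − 0.98^150 = 0.089 + 0.548 − 0.048 = 0.589.

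All scenarios (first figure N = 200, second N = 150):

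| Positivity | Expected positives, N = 150 to 200 | c = 10% | c = 20% | c = 30% | c = 41.1% |
|---|---|---|---|---|---|
| 1% | 1.5–2 | 85–90% | 74–82% | 66–76% | 61–73% |
| 2% | 3–4 | 68–76% | 47–59% | 34–48% | 27–41% |
| 5% | 7.5–10 | 37–47% | 13–22% | 5–11% | 2–6% |
| 10% | 15–20 | 13–22% | 2–5% | 0.2–1% | 0.2% or less |
| 20% | 30–40 | 2–5% | 0.2% or less | under 0.1% | under 0.1% |

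**Bias when the model does fit.** All 2x2 tables were enumerated with their exact probabilities. For maximum likelihood, log(ad/bc) was averaged over tables with no empty cell. For a single binary exposure, Firth's fit equals adding 0.5 to each cell, and it was averaged over all tables with at least one positive and one negative placenta. With c = 20% and a true log odds ratio of 0:

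| Positivity | ML, N = 150 / 200 | Firth, N = 150 / 200 |
|---|---|---|
| 2% | 0.79 / 0.62 (OR 2.20 / 1.85) | 0.32 / 0.23 (OR 1.38 / 1.26) |
| 5% | 0.22 / 0.08 (OR 1.25 / 1.08) | 0.07 / 0.03 (OR 1.07 / 1.03) |
| 10% | −0.04 / −0.07 | 0.00 / 0.00 |

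The direction is not fixed. At 2% positivity, c = 41.1% and a true odds ratio of 3, the geometric-mean fitted odds ratio is 2.06 (N = 150) or 2.28 (N = 200).

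**Precision.** With k positives and c = 20%, the Wald 95% interval extends either side of the odds ratio by the factor exp{1.96 × √[1/(0.2k) + 1/(0.8k) + 1/(0.2(N−k)) + 1/(0.8(N−k))]}. This is about 12 for k = 4 and about 5 for k = 10.

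**False positives.** The two-sided 5% Wald test was enumerated under a true odds ratio of 1. At 2% positivity and c = 20%, it rejects in 2.3–3.0% of tables that fit. Over the whole grid, the rate counting unfitted tables as non-rejections never exceeds 5%. Among fitted tables it exceeds 5% only at c = 10% with positivity of 5% or less, with a maximum of 8.7%.

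**The case against.** The strongest reply is that few positives is an assumption. One negative placenta says almost nothing about a rate, and the three other placentas in section 1.6 were assessed for morphology, not RNA. Section 1.5 argues that ddPCR detects low viral loads better than the RT-PCR used in earlier reports. At 10% positivity or more, failed fits are uncommon unless complications are rare. This stands, and it makes the point conditional. It does not remove the need for a fallback, because nothing in the documents rules out 1–5%.

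Four stronger readings are tempting and are not supported:

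- **The model is unadjusted and therefore confounded.** Section 4.2.1 is silent on covariates; the word binary describes the outcome. Confounding is a risk of unknown size. As an illustration under no true effect and 15% base risk, a factor with odds ratio 3 present in 40% of positives and 20% of negatives gives a crude odds ratio of 1.27; with odds ratio 4 and 60% against 20%, it gives 1.75.
- **Spurious associations will be declared.** The false-positive rates above do not show this in general. An odds ratio near 2 with an interval spanning a factor of 5 to 12 either way would not normally be read as an association.
- **Twins will be counted as independent rows.** The entry "Multiple births (both dichorionic and monochorionic" in section 3.9 belongs to the list of control placentas, for which slides and pathology reports are requested. Nothing places them in this regression or says that rows are infants.
- **This is the plan's only inferential model.** The supplied text has gaps in its section numbering, so that cannot be confirmed.

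The analysis is also an addition to the descriptive summary, which answers the study objective without it. That limits the weight of the point.

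**Conclusion.** The point holds in conditional form. If about 5% or fewer of the placentas are positive, ordinary maximum likelihood carries a material risk of giving no finite odds ratio: 2–47% at 5% positivity and 27–76% at 2%, for complication rates of 10–41%. The estimates that can be fitted may be well off the truth; a true odds ratio of 1 averages 1.85–2.20 at 2% positivity and 20% complications. At 10% positivity the failure risk is 0–22%, concentrated where complications are rare, and the bias is mostly small. These figures rest on assumed positivity and complication rates, one row per woman, a placental result for every participant and N of 150 to 200. Missing placentas would make matters worse, and a sample well above 200 would ease them. The consequence is a failed or unstable secondary estimate.

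**What to change.** In section 4.2.1, replace the modelling sentence with a specification along these lines:

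- Firth-penalised logistic regression with profile penalised-likelihood 95% confidence intervals, one row per pregnancy, the outcome being any complication from a list fixed in advance.
- The 2x2 table of placental result by complication is always shown.
- Below a pre-set minimum number of positive placentas (for example 5), no model is fitted; only the table and an exact interval are reported.
- The infection-to-delivery interval (section 3.6.2) enters as a single covariate only if the numbers of positives and events support it, under a rule stated beforehand. Otherwise the odds ratio is labelled as crude. More than one covariate is not realistic with 4–10 positives. The admission-date substitute for a missing diagnosis date should be noted as a source of error in this covariate.

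This is a cheap improvement: SAP wording and a different routine, with no new data. The price is slight shrinkage of the estimate and a less familiar method. If positives turn out to be plentiful, Firth and ordinary maximum likelihood nearly coincide, so little is lost. It cures neither confounding nor the low precision that comes with few positives.
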